The anticipated study duration per subject is approximately 2 months up to approximately 6 months in case of treatment extension and exacerbation during the 30-days post-daily PE period or relapse during treatment extension.

- Screening period :
From signing of ICF until randomization
- Study drug treatment period:
Covering daily PE period (variable duration) and 30-days post-daily PE period
- Treatment extension period:
7-day extensions with maximum of 28 days, i.e., 4 x 7 days
- Open-label:
In case an exacerbation during the 30 day treatment period or a relapse during the treatment extension period occurs (first exacerbation or relapse), subject will receive open label caplacizumab together with re-initiation of daily PE and optimized immunosuppressive treatment. Caplacizumab treatment schedule and visit schedule will be the same as for the initial study drug treatment period (covering daily PE [variable duration] and 30-days post-daily PE period) and the possible treatment extension period.
- Follow-up period of 4 weeks:
A first FU visit 7 days and a final FU visit 28 days after the last day of study drug administration.

Assessments:

- Screening
 - Obtain informed consent
 - Review of eligibility criteria
 - Medical history, including TTP history (and ADAMTS-13 activity levels at admission, if available)
 - GCS

- Bleeding assessment
 - Platelet count, blood smear, serum creatinine (local lab)
 - Pregnancy test (urine or blood)
 - Demographics
 - Concomitant medication
 - AEs
- Day 1
 - Randomization
 - Study drug administration** and PE + corticosteroids
 - Platelet count, blood smear
 - LDH, serum creatinine, cTnI, ADAMTS13 activity
 - Complement factors C5a and C5b-9
 - Assessment of the neurological system (including coma, stupor, seizures, disorientation/confusion, hemiparesis/-plegia, focal deficit, agitation, dysarthria)
 - Cognitive assessment (standardized mini mental state examination [SMMSE])
 - Clinically significant TTP event
 - AEs, safety laboratory parameters, physical examination, electrocardiogram (ECG), vital signs
 - Concomitant medication
 - Bleeding assessment
 - PK, PD parameters (vWF, FVIII and RICO)
 - Immunogenicity (ADA)

Study drug treatment period (including exacerbation during 30-day post daily PE period and relapse during treatment extension period), the possible treatment extension period and FU period - see [Schedules of Assessments](#).

Statistics:**Endpoints**Primary:

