Study Visit	Week 6 (+ 7 days after end of 30-day post-daily PE period) (± 1 day)	Week 7 (+14 days after end of 30-day post-daily PE period) (± 1 day)	Week 8 (+ 21 days after end of 30-day post-daily PE period) (± 1 day)	Week 9 (+ 28 days after end of 30-day post-daily PE period) (± 1 day)	Second or subsequent recurrence visit (At the time of initiating daily PE) ^b
Study drug administration (daily) ^c	x	x	x		
Corticosteroids	x	x	x	x	
Review of patient diary	x	x	x	x	x
Neurologic assessment ^d	x	x	x	x	x
SMMSE	x	x	x	x	x
Clinically significant TTP event	x	x	x	x	x
Bleeding assessment ^e	x	x	x	x	x
Adverse events					→
Concomitant medication					→
Platelet count ^f	x	x	x	x	x
Organ damage markers ^g	x	x	x	x	x
ADAMTS13 Activity	x	x	x	x	x
PK	x	x	x	x	x
PD parameters ^h	x	x	x	x	x
Immunogenicity (ADA) ⁱ				x	x

^a The following guidance with regard to timing of assessments planned at a single visit should be followed: s.c. study drug should be dosed after all other assessments have been performed.

After the last dosing in the treatment extension period, subjects are to complete assessments of the first and last FU visit as specified in [Table 3](#).

^b Also see section [3.1.1](#)

^c Study drug treatment should be administered s.c. for additional 7-day periods with a maximum of 28 days for subjects whose ADAMTS13 activity profile remains below 10% based on weekly measurements and for subjects with other clinical signs of underlying disease.

^d Neurological assessment will include assessment of the neurological system (including coma, stupor, seizures, disorientation/confusion, hemiparesis/-plegia, focal deficit, agitation, dysarthria).

^e Bleeding assessment is a clinical assessment of signs and symptoms of bleeding (e.g., petechiae, hematuria, epistaxis, meno-metrorrhagia, bruises) performed by the Investigator.

^f Samples for platelet count will be assessed by a local laboratory.

^g Organ damage markers include LDH, Troponin I, creatinine.

^h PD parameters include RICO, vWF:Ag, and FVIII:C.

ⁱ In case of a severe and/or serious hypersensitivity reaction, an additional blood sample to characterize the reaction should be collected as soon as possible after the start of the event.

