1.2.5. SAFETY PROFILE AND RISK ASSESSMENT

The benefit and risk assessment for administration of caplacizumab, as detailed in the Investigator's Brochure, supports initiation of the proposed clinical trial.

Overall, the TITAN trial provided evidence for the clinical efficacy of caplacizumab as potential treatment for patients with acquired TTP who were receiving standard of care therapy, with respect to reducing the time-to-response (based on confirmed recovery in platelet counts) and reducing the incidence of exacerbation during treatment. These findings are expected to be predictive of tangible clinical benefits in terms of reduced mortality/morbidity. The higher incidence of relapse soon after discontinuation of caplacizumab appeared to be associated with persistent low ADAMTS13 activity (<10%), suggesting unresolved underlying auto-immune activity. The current study will evaluate whether such patients would benefit from continuing treatment with caplacizumab for a longer period after discontinuation of PE.

The safety results in study ALX-0681-2.1/10 revealed no unexpected findings in relation to adverse events. The main safety finding associated with caplacizumab treatment was an increase in bleeding-related adverse events, which was consistent with findings in previous studies and is an expected consequence of the pharmacological activity of the drug. Notwithstanding this, the majority of bleeding events in the study were mild to moderate in severity, and an equal number of subjects in each treatment arm (2 subjects per arm) had a serious bleeding related TEAE. Hence, bleeding risk appears to be acceptable in the context of the anticipated clinical benefits of caplacizumab in the TTP indication. Nonetheless, vWF can be used as antidote for caplacizumab if needed. vWF and FVIII preparations as combination products are commercially available.

With regard to immunogenicity, taking into account patient, product and disease related factors, caplacizumab was assigned a low risk class designation. In the TITAN trial, drug induced TE antibodies were detected in 9% of caplacizumab treated subjects. No immunogenicity related safety findings were reported.

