3.3. TREATMENT OF SUBJECTS

Study drug treatment:

Daily PE period

- Loading i.v. dose: subjects will receive a single loading dose of 10 mg study drug by i.v. bolus injection from 6 hours to 15 minutes prior to the first PE done after randomization; also i.v. bolus of 10 mg caplacizumab (open label) will be given prior to the 1st PE for treatment of a first exacerbation during the 30-day post daily PE period or a first relapse during the treatment extension period (without a prior exacerbation).
- Daily s.c. dose: within 2 hours of completing each daily PE, a s.c. injection of 10 mg study drug will be administered daily throughout the full duration of PE treatment.

For more details on the study drug administration, please refer to section [3.3.5](#).

It is expected that subjects are hospitalized for the duration of the daily PE period. Exceptions should be discussed with the Medical Monitor.

30-day post-daily PE period

Daily s.c. administration of 10 mg study drug will continue for a period of 30 days after stop of daily PE. No adjustment to this period will be made for tapering of PE. Study drug should be administered at approximately the same time each day. Towards the end of the daily PE period and when hospital discharge is foreseen, subjects (or caregiver) should be trained in the s.c. self-administration of the study drug under the supervision of the Investigator or designee to allow for self-administration when at home. After discharge from hospital, subjects or caregiver will need to be able to self-administer s.c. study drug. For more details, please refer to section [3.3.5](#).

Treatment extension period

Study drug treatment extension beyond the 30 days will be guided by a number of risk factors for relapse of the presenting TTP episode and must be accompanied by an optimization of the immunosuppressive treatment. Study drug treatment should be extended for subjects who in the opinion of the Investigator have persistent active underlying disease for additional 7-day periods with a maximum of 28 days. In parallel, optimization of the immunosuppressive treatment should be considered at least at the Week 3 visit of the 30-day post-daily PE period and may include reversal of corticosteroid tapering through increase or re-initiation of corticosteroid treatment, or start/continuation of other immunosuppressive treatment such as rituximab (to be used as per standard site practice).

Decision on treatment extension

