4.4 Analysis Periods and Visit Windows

4.4.1 Analysis periods

The following analysis phases are defined for this study: Screening, Treatment, Follow-up. Within these analysis phases, the following analysis periods and subperiods will be considered:

Table 1: Analysis periods

Period	Subperiod	Start period	End period
(Screening)		Date of signing the ICF, with 00:00 added as timepart	First DB treatment administration datetime – 1 min
Double-Blind (DB) Treatment	Daily PE	First administration datetime of DB treatment	Start of DB post-daily PE subperiod – 1 min
	Post-daily PE	Date of switch to post-daily PE + 1 day with 00:00 added as timepart	Min(Week 5 visit date if no treatment extension or last visit date of treatment extension period with 23:59 added as timepart, early termination visit date with 23:59 added as timepart, first administration datetime of OL treatment – 1 min)
	Daily PE	First administration datetime of OL treatment	Start of OL post-daily PE subperiod – 1 min

CONFIDENTIAL

Open-label (OL) Treatment	Post-daily PE	Date of switch to post-daily PE + 1 day with 00:00 added as timepart	Min(Week 5 visit date if no treatment extension or last visit date of treatment extension period, early termination visit date) with 23:59 added as timepart
(Follow-up)		End of treatment period + 1 min	Trial termination date, with 23:59 added as timepart

Note that the last analysis period in case of early termination will always be ended by the trial termination date.

The 'overall treatment period' corresponds with the treatment analysis phase and covers both the DB treatment analysis period and the OL treatment analysis period. Note that only subjects who experience a relapse or exacerbation will have an OL treatment analysis period. For these subjects, the overall treatment period starts at start of DB treatment period and ends at end of OL treatment period. For subjects with no switch to open-label caplacizumab, the overall treatment period starts at start of DB treatment period and ends at end of DB treatment period.

The 'overall study period' covers both the treatment analysis phase and the follow-up analysis phase.

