 Tabulation of TEAE preferred terms per system organ class and per analysis period. Selecting only the thromboembolic TEAEs.

Population: safety population.

Table 14.3.1.15: Treatment-emergent adverse events: Tabulation of all hypersensitivity reactions

Tabulation of TEAE preferred terms per system organ class and per analysis period. Selecting only the hypersensitivity reactions.

Population: safety population.

Table 14.3.1.16: Treatment-emergent adverse events: Tabulation of all treatment-related hypersensitivity reactions

Tabulation of TEAE preferred terms per system organ class and per analysis period. Selecting only the hypersensitivity reactions that were treatment-related (as defined in Section 7.1.1).

Population: safety population.

Table 14.3.1.17: Treatment-emergent adverse events: Tabulation of all adverse events by subgroup

Tabulation of TEAE preferred terms per system organ class by subgroup. Following subgroups will be shown:

- Treatment extension (yes/ no)
- Baseline disease severity (very severe/ less severe)

Population: safety population.

Table 14.3.1.18: Treatment-emergent adverse events: Tabulation of all serious adverse events by subgroup

Tabulation of serious TEAE preferred terms per system organ class by subgroup. Following subgroups will be shown:

- Treatment extension (yes/ no)
- Baseline disease severity (very severe/ less severe)

Population: safety population.

Table 14.3.1.19: Treatment-emergent adverse events: Tabulation of all bleeding events by subgroup

Tabulation of bleeding event preferred terms per system organ class by subgroup. Following subgroups will be shown:

- Treatment extension (yes/ no)
- Baseline disease severity (very severe/ less severe)
- Antithrombotic agents (yes / no), this subgroup will be based on MedDRA coding (ATC term Antithrombotic Agents, ATC codes starting with B01A).

Population: safety population.

Table 14.3.1.20: Treatment-emergent adverse events: Tabulation of all thromboembolic events by subgroup.

Tabulation of TEAE preferred terms per system organ class and per analysis period (including number of events and incidence per 100 patient months) by subgroup. Following subgroups will be shown:

Refractory TTP (yes / no)

Population: safety population.

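### Adverse events that start during the treatment extension get no table of their own, and the extended-versus-not-extended safety tables cover unequal observation time

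*SAP*

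**What the plan says.** Protocol 3.3 sets a fixed dosing phase: "Daily s.c. administration of 10 mg study drug will continue for a period of 30 days after stop of daily PE". The Protocol synopsis, under study duration, then describes a separate extension period: "7-day extensions with maximum of 28 days, i.e., 4 x 7 days". This period has its own schedule (Protocol Table 4, Weeks 6 to 9). Protocol 1.2.5, referring to patients with persistently low ADAMTS13 activity, says: "The current study will evaluate whether such patients would benefit from continuing treatment with caplacizumab for a longer period after discontinuation of PE". SAP section 1 makes the same statement.

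SAP 4.4.1, Table 1, divides double-blind and open-label treatment into two subperiods each, daily PE and post-daily PE. The double-blind post-daily PE subperiod ends at the earliest of three times: the "Week 5 visit date if no treatment extension or last visit date of treatment extension period with 23:59 added as timepart", the early termination visit, or the first open-label dose. The open-label subperiod ends at the earlier of "Week 5 visit date if no treatment extension or last visit date of treatment extension period, early termination visit date".

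SAP 7.1.2 lists the periods for all AE tables: daily PE and post-daily PE for each of double-blind and open-label treatment, then overall treatment, follow-up and overall study. There is no extension period. SAP 7.1.1 puts each event in the period where it started and bases percentages on the subjects still in the study in that period.

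SAP 14.6 plans three AE tables, 14.3.1.17 (TEAEs), 14.3.1.18 (serious TEAEs) and 14.3.1.19 (bleeding), by "Treatment extension (yes/ no)". Incidence per 100 patient months is specified for the general summary, which is not split by extension, and for Table 14.3.1.20, which is split by refractory TTP. It is not specified for the three extension tables.

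**The concern.** The Phase II trial gave study drug during daily PE and for 30 days afterwards (Protocol 1.2.4), so the extension adds exposure beyond that trial. Bleeding is the main safety finding named in Protocol 1.2.5. A reader of the study report will want to know how many bleeding events began in the added weeks, in how many subjects at risk and over how much time. The visible tables do not answer this, because extension events are pooled with those of the preceding 30 days.

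The yes/no tables look like the answer but measure something else. An extended subject is observed longer, and all of that subject's earlier events also count under *yes*. A double-blind *yes* requires reaching the end of the 30 days, whereas subjects who stopped permanently before then fall under *no*. A difference between the groups therefore mixes risk, observation time and selection. What is at stake is a wrong impression of the safety of longer dosing, in either direction.

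**Working it through.** The plan states no figure on this point, so there is none to reproduce. The check concerns window lengths and what they alone would produce.

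**Inputs**
- Fixed post-daily PE dosing: 30 days (Protocol 3.3).
- Extension length e: 7, 14, 21 or 28 days (Protocol synopsis).
- Window ends: SAP 4.4.1, Table 1.
- Follow-up: 28 days after the last dose (Protocol synopsis).
- Daily PE: 6 days, assumed for illustration. The Phase II means were 5.9 days on caplacizumab and 7.9 on placebo (Protocol 1.2.4).
- 30-day incidence p: 10%, 30% and 50%, all assumed, because the documents give none for this window.

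**Step 1: window length, extended against not extended**
- Post-daily PE: (30 + e) against 30, so 37, 44, 51 or 58 days against 30. Ratios are 1.23, 1.47, 1.70 and 1.93.
- Overall treatment: (36 + e) against 36, so 43 to 64 days against 36. Ratios are 1.19 to 1.78.
- Overall study: (64 + e) against 64, so 71 to 92 days against 64. Ratios are 1.11 to 1.44.

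These figures take a non-extended subject who completes the 30 days. Those who stop early or switch have shorter windows.

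**Step 2: effect of length alone.** With the same constant hazard in everyone, the share of subjects with an event over 30 + e days is 1 − (1 − p)^((30 + e)/30).

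| Assumed p over 30 days | 37 days | 44 days | 51 days | 58 days |
|---|---|---|---|---|
| 10% | 12.2% | 14.3% | 16.4% | 18.4% |
| 30% | 35.6% | 40.7% | 45.5% | 49.8% |
| 50% | 57.5% | 63.8% | 69.2% | 73.8% |

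For p = 30% and e = 28: 1 − 0.70^(58/30) = 0.498, an apparent excess of about 20 points with no change in risk. With e = 7 the excess is about 6 points.

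**Step 3: would the SAP's rate cure it?** SAP 7.1.2 divides subjects with an event by all months observed, including time after the event. At p = 30% and 30.4375 days per month, this gives 100 × 0.300/(30/30.4375) = 30.4 over 30 days and 100 × 0.498/(58/30.4375) = 26.1 over 58 days. It removes most of the artefact but leaves a smaller one in the opposite direction. At p = 10% the figures are 10.1 and 9.7.

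**Step 4: dilution in the merged window.** If a fraction f of subjects extends by the full 28 days (assumed), extension time is 28f/(30 + 28f) of post-daily PE time. That is 8.5% for f = 10%, 19% for f = 25% and 32% for f = 50%. A change in risk during the extension would be hard to see in the pooled subperiod.

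**Step 5: after a split at Week 5.** Every subject who completes the 30 days contributes about 30 days to the first part, so the window ratio becomes 1.00. At constant hazard both groups then show 30%. The further 7 to 28 days are reported separately.

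**The case against.** The strongest reply is that this is a matter of presentation. AEs are collected throughout, and a bleeding assessment is scheduled at each of Weeks 6 to 9 (Protocol Table 4). Listings 16.2.7.1 and 16.2.7.6 carry the onset information from which an extension window can be derived. The yes/no tables have no test, and results are shown by treatment group, so within *yes* the reader sees caplacizumab beside placebo under the same maximum extension. Daily PE and follow-up events are already separated. Protocol 1.2.5 speaks of benefit, and no objective in Protocol section 2 concerns the safety of the extension. Finally, SAP 7.1.3 on exploratory AE analysis is empty in the public text and might hold more.

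Most of this stands, and it limits the point to the display of safety data. It does not remove it. Table 1, the period list and the consecutively numbered AE table index are all visible, and none shows events by onset in the extension. A side-by-side table invites comparison with or without a test.

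A reader might infer more than the documents support:
- *That the trial cannot describe bleeding risk in the added weeks.* It can, from data already collected; the planned tables do not do so.
- *That a subject with an exacerbation always counts as* no. After a first exacerbation the open-label course may itself include an extension (Protocol synopsis), and SAP 5.6 counts extensions in the open-label group. The real gap is that the tables do not say which extension defines *yes*.
- *That these are the only displays by extension.* Table 14.3.5.7 gives immunogenicity by extension, and SAP 5.6 counts extended subjects. The statement here is confined to AE tables.

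**Conclusion.** The point holds as a fault in the safety display. The merge in Table 1 and the missing period follow directly from the text. The yes/no tables compare about 30 days with 37 to 58 days of post-daily PE time on a status set after baseline. Under a constant hazard and an assumed 30-day incidence of 30%, length alone turns 30% into 36% to 50%. The size depends on that assumed incidence, on how long subjects are extended and on which period column is read; it is smaller over the overall study period. Selection of early stoppers into *no* is not quantified and can offset or reverse the effect, so the net direction is unknown. The primary endpoint and the confirmatory tests are unaffected. The change is worth making because it is cheap and the extension is exposure that the trial itself introduced.

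**What to change.** 1. In SAP 4.4.1, Table 1, split each double-blind and open-label post-daily PE subperiod at the Week 5 visit into a 30-day part and an extension part, and add both to the period list in SAP 7.1.2.
2. Report TEAEs, serious TEAEs and bleeding events with onset in each part, by treatment group, with subjects at risk, number of events and incidence per 100 patient months. A footnote should say that the SAP formula counts time after the first event.
3. If Tables 14.3.1.17 to 14.3.1.19 are kept, restrict them to subjects still on study drug at the Week 5 landmark, count only events from that point, and give them per patient-time. State whether a double-blind or an open-label extension defines *yes*.

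The cost is modest programming on AE onset dates and period dates already collected (Listings 16.2.1.3 and 16.2.7.1). No data collection, treatment rule or extension rule changes. Numbers in the extension part may be small. Entry to it follows ADAMTS13 activity and the investigator's judgement after randomization, so the arm comparison there remains descriptive.

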4.4.2 Relative number of days

The relative day (DY) is calculated as follows:

- = Visit date – reference date + 1 day, when the visit date is on or after the reference date
- = Visit date – reference date, when the visit date is before the reference date.

The reference date is the date of first intake of the study drug, which by definition has DY=1. There is no DY=0.

4.5 Software and validation model

4.5.1 Software

SAS version 9.2 will be used for programming.

4.5.2 Validation model

Currently valid [REDACTED] SOPs will be followed.

The ADaM datasets and tables will be validated following Model C; listings and figures follow validation model B ([REDACTED]):

- Model B: review of the output, source code and program log by an independent person (i.e., somebody different from the developer).
- Model C: independent programming of the parameters indicated in this SAP.

